The present study will elucidate whether the presence of five common radiological bowel signs on CT, either alone or in combination, may distinguish between no bowel ischaemia (suspected AMI) vs. reversible (AMI treated without bowel resection) vs. irreversible ischaemic damage (AMI treated with bowel resection).

To accomplish this, CT scans from patients enrolled in the multicentre international study (The AMESI study, Clinical Trials: NCT05218863) will be collected and subjected to retrospective analysis by the investigating radiologists. After analysing predefined radiological signs separately for their association with the need for bowel resection, the feasibility of combining different CT findings will be explored with the goal of **establishing a practical CT-based radiological scoring system for separating patients with reversible and irreversible bowel ischaemic damage.**

As different subtypes (arterial, venous, and non-occlusive mesenteric ischemia) have different pathoanatomical courses, differences in radiological bowel signs may be expected. To overcome this variability, we will first elaborate the score based on all patients with a confirmed diagnosis of AMI. As a second stage, we will test the score by including only patients with arterial occlusive AMI. If these two created scores appear to be different, we will test them mutually and in subgroups of other subtypes of AMI. The ultimate goal is to have one radiological score identifying the magnitude of bowel damage that could be used for any form of AMI, with possible minimized adaptations needed subtypes.

Considering the low number of venous AMI and NOMI we will primarily not create separate scores for these subtypes. If the performance of created scores appears insufficient in our study, these subtypes need to be assessed in a separate study.

Objectives

The primary objective of the study is to **create a CT-based AMI score using radiological signs that would enable the differentiation between patients with salvageable and non-salvageable ischemic bowel damage.**

The specific objectives are as follows:

- To describe the prevalence of common radiological bowel signs (Table) in AMI patients with and without irreversible ischaemic damage of the bowel.
- To assess the prognostic capability of these radiological bowel signs, both individually and in combination, for predicting irreversible ischaemic damage of the bowel.

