- To describe the prevalence of common radiological bowel signs in patients with confirmed AMI vs. suspected but eventually non-confirmed diagnosis of AMI
- To describe the prevalence of common radiological bowel signs in patients with different subtypes of AMI (arterial occlusive, venous, NOMI, other/unclear).

Study questions

- 1) What is the frequency rate of common radiological bowel signs (Table 1) among AMI patients with and without salvageable bowel?
- 2) Is it possible to distinguish the AMI patients with and without salvageable bowel with the use of a CT-based AMI score composed of common radiological signs?
- 3) Is it possible to differentiate the patients with and without AMI with the use of CT-based AMI score composed from common radiological signs?

Hypothesis

It is possible to differentiate between AMI patients with salvageable and non-salvageable ischemic bowel damage using the score based on CT radiological bowel signs.

Study outcomes

Primary study outcomes: Frequency rate of common radiological signs in AMI patients with and without salvageable bowel. Radiological score value in AMI patients according to the stage of bowel ischaemic damage.

Secondary study outcomes:

Frequency rate of common radiological signs/findings among patients with confirmed and suspected but eventually not confirmed AMI.

Performance of the radiological score in patients with different types of AMI.

Methods

This is a substudy of the AMESI study - "Incidence, Diagnosis, Management, and Outcome of Acute Mesenteric Ischaemia: A Prospective, Multicentre Observational Study." As of the end of August 2023, a total of 705 patients from 32 study sites worldwide have been enrolled, with 418 of them having confirmed cases of AMI. For patients with confirmed AMI, comprehensive data collection concerning diagnostics, management, and long-term outcomes has been completed (refer to Appendix 1).

Patients:

From the final AMESI cohort, we will select 6-7 sites limited to Europe due to logistical reasons related to the installation of software for the transmission of full CT investigations in impersonalized form. We expect to obtain images of at least 100 patients with confirmed AMI. Only study sites with more than 20 patients in total enrolled in the study will be asked to contribute radiological data. The CT scans will be gathered through AMESI's dedicated international online platform, and a retrospective visual and

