The AMESI database of pseudonymized CT-s can be accessed via an online platform with the personal identification of selected and authorized study group members. For participants in the AMESI study, the consent to use the clinical and imaging data has been obtained or waived at enrolment, based on local ethics rules. A centralized collection of radiological images was planned in the study protocol of the AMESI study. Installation of software for pseudonymizing CT images will require additional institutional approval from each site.

Data collection:

Patients' clinical and demographic characteristics, including baseline data, AMI event data, management data, histology data, and hospital outcome data will be retrieved from the RedCap database of the AMESI study (Appendix 2), or from the Tartu University Hospital patient data management system.

Data Retention:

The data collected during the study will be stored securely on Tartu University servers till 31.12.2039 and will be securely removed after this date. Only authorised study team members will have access to the data.

Allocation of patients into study groups:

To test the hypothesis, the study patients will be divided into the following study groups:

	Control Cases	Patients with confirmed AMI. Target: 100 - 200	
		AMI patients with salvageable bowel	AMI patients with non-salvageable bowel
No of pt	Target: 50-100	Target: 50-100	Target: 50-100

Definition of the patient group	Patients included in the AMESI study as suspected AMI	Patients included in the AMESI study with confirmed AMI, who did not undergo bowel resection Patients with one of the following:	Patients included in the AMESI study with confirmed AMI who (one of the following): 
 1) treated endovascularly and did not undergo bowel resection secondarily 2) received surgical revascularization without bowel resection (initial or secondary) 3) received explorative laparoscopy or laparotomy without the need for bowel resection (initially or secondarily) 4) received conservative treatment without the need for secondary bowel resection
---------------------------------	---	--	---

Radiological Methods:

CT scans with intravenous contrast media relevant to the hospitalization of selected patients from the AMESI study cohort will be pseudonymized and uploaded to the online AMESI database. The selection of CT scans will be based on the initial diagnostic hypothesis of acute abdomen or suspicion of AMI.

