Inclusion Criteria: CT scan of the entire abdominal cavity / full body using intravenous contrast media.

Exclusion criteria: Scans without the use of an intravenous contrast media or those covering only a partial area of the abdomen will be excluded.

Two radiologists, who will be blinded to the original radiology report, clinical diagnosis and outcome of the patient, will review the CT scans. The CT images will be screened for radiological signs indicative of mesenteric ischaemia (Table 1). The presence of these signs will be recorded as indicated in the Table. In order to develop a radiological score, the bowel signs are used.

Statistics

Obtaining radiological data:

Interobserver agreement for CT findings will be determined with the κ statistic and classified as follows: $\kappa = 0\text{--}0.2$, slight agreement; $\kappa = 0.21\text{--}0.4$, fair agreement; $\kappa = 0.41\text{--}0.6$, moderate agreement; $\kappa = 0.61\text{--}0.8$, substantial agreement; and $\kappa = 0.81\text{--}1$, almost perfect agreement.

Disagreements between the two reviewers will be resolved by consensus. Consensual data will then be used for final statistics.

Descriptive statistics:

We will compare epidemiological data and CT signs between patients with and without salvageable bowel damage. Pearson Chi-square or Fisher tests will be used for the comparison of categorical variables, and the Student t-test or Wilcoxon rank-sum test for the comparison of continuous variables as appropriate. A frequency table for the occurrence of radiological symptoms in study groups will be constructed.

Workout of radiological CT-score

In order to develop a radiological score, the bowel signs are used (Table 1, 3-7). We will compare CT signs

- 1) between the patients with salvageable and non-salvageable bowel damage;
- 2) between the patients with confirmed and suspected but eventually not confirmed AMI. The conceptual approach is presented in Figure 1.

[figure not shown]

Figure 1. Conceptual approach for radiological score.

Pearson Chi-square or Fisher tests will be used for the comparison of categorical variables, and Student t-test or Wilcoxon rank-sum test for the comparison of continuous variables as appropriate.

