All CT findings with a univariate p -value ≤ 0.1 were entered into a multivariate logistic regression model to gauge their independent association with non-salvageable bowel damage (comparison 1) or confirmed diagnosis of AMI (comparison 2). The radiological score will be constructed based on univariate logistic regression models, where the dependent variable will be non-salvageable bowel and the independent variable will be radiological sign. The number of models will be equal to the number of radiological signs. The coefficient from the model will be uprounded and used as a weight for the radiological sign. In case the weights from the univariate models are clinically not relevant, expert opinions will be used instead. All the radiological signs will then be multiplied with the assigned weights and then summed. Finally, one by one the radiological signs will be left out of the score to test, whether a simpler version of the score would also give as good results as the more complicated version. The goodness of the score will be evaluated using AUC. A similar score will be constructed for suspected vs confirmed AMI.

However, if this will not result in a useful score, we will use a more complicated approach based on interactions between the radiological signs and interpretations of the results from the simpler approach.

In the first approach, **two scores** will be constructed.

- 1) using data of all patients with confirmed AMI
- 2) using data of only patients with confirmed arterial occlusive AMI

The performance of these two score will be tested in the following cohorts:

- a) all patients with confirmed AMI
- b) only occlusive arterial AMI included
- c) only non-occlusive AMI included
- d) Patients with venous occlusive AMI excluded
- e) Patients subjected to palliative care excluded

Table 1. Common radiological signs used to detect bowel ischaemia in CT imaging

	Radiological sign	Description
Vascular signs:		
1.	Occlusion of superior/inferior mesenteric artery/or its respective branches	No contrast enhancement on MDCT scan in the arterial phase or in the venous phase/lack of contrast enhancement within the vessel lumen / Acute arterial thrombi and emboli may appear as obvious low-attenuation filling defects in the SMA, its branches, or other major mesenteric arteries.

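### After an undefined 'not useful' result the plan moves to a sign-interaction score judged in the same patients, so its AUC is optimistic precisely when the signs look weak

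*Protocol*

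**What the plan says.** The Hypothesis section commits to one claim: "It is possible to differentiate between AMI patients with salvageable and non-salvageable ischemic bowel damage using the score based on CT radiological bowel signs".

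Under Statistics, in the part on working out the CT score, each sign is first put into its own logistic model: "The coefficient from the model will be uprounded and used as a weight for the radiological sign". The weighted signs are summed, signs are then dropped one at a time, and "The goodness of the score will be evaluated using AUC". The next paragraph adds the escalation: "However, if this will not result in a useful score, we will use a more complicated approach based on interactions between the radiological signs". That sentence goes on to say that interpretation of the simpler results will also feed the new approach.

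Scores are built from all confirmed-AMI patients and from the arterial occlusive ones alone. They are then tested in five cohorts, (a) to (e). Cohort (a) is all confirmed AMI, which is the set that builds the first score. The other four are subsets of it.

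The numbers available are an expectation ("We expect to obtain images of at least 100 patients with confirmed AMI") and a target ("Patients with confirmed AMI. Target: 100 - 200"), with 50-100 in each of the salvageable and non-salvageable groups.

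**The concern.** The trigger for the second approach is the result of the first, and nothing says what result pulls it. The second approach is more flexible, it may be shaped by what the first one showed, and the protocol describes no data for judging it other than the patients who produced it.

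Apparent AUC does not fall when terms are added in the ordinary course of fitting, whether or not the terms carry information. The rule therefore applies the most optimistic method in just those studies where the signs look least informative. This comes on top of the usual optimism of the simple score, because it is a written rule that operates only after disappointment.

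At stake is a score meant to help separate patients who need bowel resection from those whose bowel can be saved. A fallback score could look better on paper than the simple one and discriminate no better, or worse, in new patients.

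**Working it through.** The protocol gives no sample-size calculation, target AUC or expected sign frequencies for the study, so there is no figure of its own to reproduce. The check is a simulation under stated assumptions.

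**Inputs from the protocol**
- Signs: five. The Background asks "whether the presence of five common radiological bowel signs on CT, either alone or in combination", and the Statistics section says "In order to develop a radiological score, the bowel signs are used (Table 1, 3-7".
- Patients: 100-200 with confirmed AMI, 50-100 per group. The settings are 50 v 50, 75 v 75 and 100 v 100.

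**Assumptions the protocol does not fix**
- Every sign is unrelated to outcome.
- Sign prevalences are 10-50%, with latent correlation between signs of 0 or 0.3.
- The fallback keeps all two-way interactions.
- An AUC of 0.70 counts as 'useful'.

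**Size of the assumed fallback.** Two-way interactions: 5 x 4 / 2 = 10. Terms: 5 + 10 = 15. With 50 non-salvageable patients, that is 50 / 15 = 3.3 per term.

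**Method.** There were 500 null studies per setting. The simple score is the sum of sign times univariate log-odds coefficient, with raw and rounded weights. The fallback is a logistic model with 15 terms. A third version keeps only those of the 15 terms with univariate p<=0.1. AUC is computed in the same patients.

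| Patients | Simple: mean AUC | Simple: share >=0.70 | All ten interactions: mean AUC | All ten: share >=0.70 | Only terms with p<=0.1: share >=0.70 |
|---|---|---|---|---|---|
| 50 v 50 | 0.56-0.62 | 0-3% | 0.69-0.72 | about 40-67% | 0.4-4% |
| 75 v 75 | 0.54-0.60 | at most 0.2% | 0.66-0.68 | 8-23% | at most 1% |
| 100 v 100 | 0.54-0.59 | 0% | 0.63-0.65 | 1-5% | at most 0.2% |

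Ranges run over the prevalence and correlation settings. At 50 v 50, the lower end belongs to settings with several rare signs (10-15%) and the upper end to prevalences of 30-50%. Monte Carlo standard error near 62% is sqrt(0.62 x 0.38 / 500) = 0.022, about 2 percentage points.

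**Two sensitivity checks**
- *Fewer interactions.* Keeping only the three interactions that raise AUC most (300 null studies per setting, prevalences 20-50%) gave 44%, 10% and 2% reaching 0.70 at the three sizes.
- *A different bar.* At 0.65 and 100 v 100, the simple score gets there in about 1-2% of null studies and the full interaction model in about 45-47%. This is not comparable with the 0.70 column. It shows how far the answer depends on a bar that the protocol leaves open.

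**Weak but real signs.** With assumed sign rates of 50/45/25/20/25% against 42/36/20/15/20% at 50 v 50, moving from the simple score to the full interaction model raised mean apparent AUC from 0.64 to 0.73. In new patients mean AUC fell from 0.55 to 0.53.

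**The case against.** The strongest reply is that the large figures belong to an assumed model at the smallest planned size. The protocol speaks only of an approach based on interactions, which could mean one or two clinically chosen combinations. With p<=0.1 selection the effect nearly vanishes. This stands, and so the figures are given as a conditional range. The limit to it is that the protocol attaches no such filter to the fallback.

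A second reply is that signs of no value are not the expected case. The Background cites specificity up to 98% and sensitivity of 30-40% for single signs. In equal groups that implies prevalence between (0.30 + 0.02) / 2 = 16% and (0.40 + 0.02) / 2 = 21%. With five independent signs of 30-40% sensitivity and 90-98% specificity (an assumption), the simple score's mean apparent AUC is 0.79-0.95 and the fallback would rarely be called on. This also stands. The null is a stress test, but the rule exists for the case where the signs disappoint, and its behaviour there is what needs judging.

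Third, this is a feasibility substudy, the fallback is declared in advance, no studied patient's care is affected, and a statistical analysis plan that is not at hand may add validation. That lowers the severity. It does not remove the point, because the protocol itself lays down the switch and same-patient testing.

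A reader might go further and infer three things that the document does not support:
- *That useless signs would reach 0.70 in about 6 of 10 studies.* This holds only near 50 v 50, with signs that are not rare and all ten interactions kept. At 100 v 100 it is 1-5%.
- *That the hypothesis cannot fail.* At 100 v 100, 95-99% of null studies stay below 0.70 even with all ten interactions.
- *That a failed simple score would go unreported.* The protocol does not say so, and it uses the simple results as input to the fallback.

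**Conclusion.** The point holds in a limited form and should be fixed. The protocol fixes a results-triggered move to a more flexible score, leaves 'useful' undefined, and describes testing only in the development patients or subsets of them. The direction of the bias is certain: the fallback's apparent AUC will be optimistic.

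Its size is not certain. Under the assumptions listed, it ranges from large at the lower patient target to small at the upper one, and it is small throughout if terms are filtered by p-value. The arterial-only score uses fewer patients, so its optimism would be greater, but the protocol gives no number for that subgroup.

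**What to change.** Amend the paragraph on working out the score to state four things:

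1. 'Useful' means a threshold, named beforehand, on the optimism-corrected AUC of the simple score.
2. The simple score's AUC with its confidence interval is the answer to the hypothesis and is reported whatever its value.
3. Any interaction-based score is exploratory and is shown beside the simple score, not in its place.
4. The AUC of an interaction-based score is given only after a bootstrap correction that repeats the whole model building in each resample, including the decision to switch. That requires the switch and the choice of interactions to be written as rules a program can follow.

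No new data are needed. The cost is a few sentences and a little more analysis code. The downside for the investigators is that a weak simple-score result must then be reported as the main answer.

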2.	Occlusion of superior mesenteric vein/or branches	No contrast enhancement on MDCT scan in porto-venous phase/lack of contrast enhancement within the vessel lumen / The thrombosed superior mesenteric vein is seen as a large, distended vessel that does not fill appropriately with contrast / a low-attenuation filling defect on contrast-enhanced CT.
Bowel signs:		
3.	Bowel dilatation	
Abnormal dilatation of small or large bowel loops compared to the adjacent normal bowel loops. Evaluation of 3 different bowel segments is carried out – small bowel, large bowel and caecum.
 
Abnormal dilatation is considered if the diameter is:
 
- >30 mm for small bowel- >60 mm for large bowel- >90 mm for caecum 
Documentation of the findings:
 
1. No bowel dilatation2. Unsure/uncertain/technically difficult to evaluate3. Bowel dilatation present by radiologist assessment, specify the bowel segment

		
4. Maximum bowel diameter in mm in three locations: small bowel, caecum large bowel, caecum
 
Classification of the findings on bowel diameter will be worked out through the analysis of the results. First, cut-off values of bowel dilatation for prognostication of unsalvageable bowel for each segment under review will be identified. Second, Their weights will be identified and incorporated into the score.

4.	Decreased, absent or abnormal bowel wall enhancement	
No contrast enhancement, segmental enhancement decrease of bowel loops in comparison with adjacent normally enhancing bowel loops or abnormal hyperenhancement of bowel loops.
 
Documentation of the findings:
 
 1. Normal bowel wall enhancement 2. Unsure/uncertain finding/technically difficult to evaluate 3. Hyperenhancement of the bowel wall 4. Decreased/diminished enhancement 5. No enhancement in the venous phase 
Evaluation of bowel wall enhancement will be documented in two different ways:
 
 1. Small bowel, large bowel and caecum wall density is measured and documented in Hounsfield units (HU) 2. Visual evaluation of 4 quadrants of the abdomen and identifying visual differences of segmental bowel wall enhancement in comparison to adjacent bowel loops. If a difference is identified the segmental HU values are measured in visually normal and altered bowel loops. The significant difference is analysed further statistically.

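### The CT scores are tested almost entirely in the patients used to build them, so the planned AUC is an apparent value, biased upwards

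*Protocol*

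**What the plan says.** Under Statistics, Workout of radiological CT-score, the protocol plans two scores, one "using data of all patients with confirmed AMI" and one "using data of only patients with confirmed arterial occlusive AMI". It continues: "The performance of these two score will be tested in the following cohorts". The cohorts are (a) all confirmed AMI, (b) arterial occlusive only, (c) non-occlusive only, (d) venous occlusive excluded and (e) palliative care excluded.

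Several steps that use the outcome come before that evaluation:

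- **Cut-offs.** Table 1, sign 3 (bowel dilatation): "cut-off values of bowel dilatation for prognostication of unsalvageable bowel for each segment under review will be identified". Three segments are under review.
- **Weights.** Univariate logistic coefficients against non-salvageable bowel are rounded up. There is an override: "In case the weights from the univariate models are clinically not relevant, expert opinions will be used instead".
- **Dropping signs.** "one by one the radiological signs will be left out of the score to test" whether a simpler score does as well.
- **Fallback.** "if this will not result in a useful score, we will use a more complicated approach", based on interactions.

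The yardstick is given in one sentence: "The goodness of the score will be evaluated using AUC". The Background section also speaks of testing the score in arterial patients and, if the two scores differ, of testing them mutually and in other subtypes. All of these patients come from the same confirmed AMI set, with a target of 100 to 200.

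**The concern.** An AUC computed in the patients who supplied the cut-offs, the weights and the choice of signs rewards the score for fitting chance features of those patients. On average it is higher than the AUC the same score would reach in new patients. The gap grows as the sample shrinks and as more choices are made by looking at the outcome.

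The primary objective is to create a score that separates salvageable from non-salvageable bowel, and AUC is the only stated measure of whether the score is good. Three decisions lean on it: whether the score is useful, whether a simpler version is as good, and how the two scores compare. The last has an added bias. In cohort (b) the arterial score was fitted to exactly those patients, so it tends to look better there even when it is not.

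**Working it through.** The protocol gives no target AUC, sample-size calculation or expected optimism, so there is no figure of its own to reproduce.

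**Step 1: overlap between development and test patients**

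| Cohort | Score 1 (built on all AMI) | Score 2 (built on arterial AMI) |
|---|---|---|
| (a) all confirmed AMI | its own development set | contains its development set |
| (b) arterial only | development patients only | its own development set |
| (c) non-occlusive only | development patients only | **disjoint** |
| (d) venous excluded | development patients only | contains its development set |
| (e) palliative excluded | development patients only | overlaps |

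Score 1 is evaluated in its own patients in 5 of 5 cohorts and score 2 in 4 of 5, so 9 of 10 evaluations reuse development patients. The exception, score 2 in (c), concerns a subtype that the Background describes as low in number. It is not clean either if the dilatation cut-offs are set on all AMI patients; the protocol does not say on which set they are found.

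**Step 2: simulation of the written steps**

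*Inputs from the protocol.* 50 to 100 patients per bowel group (Allocation of patients into study groups); single-sign sensitivity 30–40% and specificity up to 98% (Background).

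*Assumed.* Four independent binary signs plus three diameters; each cut-off maximises sensitivity + specificity − 1; a sign is dropped when the same-data AUC does not fall.

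*Formulas.* In the 2×2 table of sign by outcome, let a and b be the patients with the sign and c and d those without it, with non-salvageable bowel (a, c) or salvageable bowel (b, d).

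- Weight = ln[(a+0.5)(d+0.5) / ((b+0.5)(c+0.5))], rounded up.
- Score = sum of weight × sign.
- Excess = AUC in the development patients − AUC of the same score in 3,000 new patients.

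Means of 600 runs, Monte Carlo standard error at most 0.003:

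| Assumed signal | Per group | Apparent AUC | New-patient AUC | Excess |
|---|---|---|---|---|
| None (each sign 20% in both groups) | 50 | 0.639 | 0.500 | 0.138 |
| | 100 | 0.595 | 0.500 | 0.094 |
| Weak (sensitivity 30–35%, specificity 80%, diameters +0.25 SD) | 50 | 0.748 | 0.635 | 0.113 |
| | 100 | 0.718 | 0.646 | 0.071 |
| Stronger (sensitivity 30–40%, specificity 90–95%, diameters +0.5 SD) | 50 | 0.885 | 0.830 | 0.056 |
| | 100 | 0.872 | 0.840 | 0.032 |

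Score 2 rests on fewer patients. At an assumed 25 per group the excess is 0.100 (stronger), 0.170 (weak) and 0.211 (none).

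**Step 3: dependence on the assumptions**

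A wider simulation used correlated signs (latent correlation 0.2), 500 runs per cell and three readings of leaving signs out: drop if the AUC is not lower, drop while within 0.01 of the full score, or no dropping. Sensitivity was 30–40% throughout.

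| Signal | Specificity; diameters | Per group | Apparent AUC | New-patient AUC |
|---|---|---|---|---|
| Weak | 75–85%; +0.3 SD | 50 | 0.74–0.75 | 0.62–0.66 |
| Moderate | 85–92%; +0.4 SD | 50 | 0.81 | 0.72–0.75 |
| Moderate | 85–92%; +0.4 SD | 100 | about 0.79 | 0.74–0.75 |
| Strong | 92–98%; +0.4 SD | 50 | 0.86–0.87 | 0.79–0.82 |

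With a real signal the excess was 0.04–0.11 at 50 per group and 0.03–0.08 at 100. Repeat runs put the strong signal at 100 per group at 0.02–0.03. With no signal the excess was 0.12–0.13 and 0.08–0.09.

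**Step 4: share due to the cut-off search**

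Excess without dropping, 50 per group, searched minus fixed cut-offs:

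- none: 0.122 − 0.077 = 0.045
- weak: 0.078 − 0.031 = 0.047
- moderate: 0.058 − 0.020 = 0.038
- strong: 0.044 − 0.013 = 0.031

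**Step 5: score 2 against score 1 in cohort (b)**

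With an assumed arterial share of 50–80%, the same truth in every subtype and a real signal, score 2 looked better in 70–97% of runs and was truly better in 21–41%. The apparent gain was 0.003–0.05; the true difference was −0.002 to −0.02.

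**Step 6: how well correction works**

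| Setting | Apparent → bootstrap-corrected → true | Share of excess removed |
|---|---|---|
| Moderate, 50 per group | 0.819 → 0.765 → 0.740 | 0.054/0.079 = 68% |
| Moderate, 100 per group | 0.795 → 0.760 → 0.750 | 0.035/0.045 = 78% |
| None, 50 per group | 0.643 → 0.551 → 0.501 | 0.092/0.142 = 65% |

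Repeated 10-fold cross-validation, estimate against truth: 0.744 vs 0.740, 0.748 vs 0.749 and 0.512 vs 0.501 in the same three settings.

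**The case against.** Internal validation is often specified in a SAP, which is not at hand, and nothing in the protocol forbids correcting the AUC. That is fair, and the absence of a named resampling method is not itself the point. The protocol fixes the test cohorts, and they consist of development patients.

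The word *tested* could be read loosely, with (a) to (e) as subtype and sensitivity analyses in a feasibility study whose listed primary outcomes are sign frequencies and score values; performance by AMI type is secondary. This excuses the lack of an external cohort, which is not asked for here. It does not change what the AUC estimates.

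Two qualifications stand. If the scores differ, the Background also foresees testing in other subtypes, so venous AMI would be a second disjoint set for score 2. And the stated goal is one score for any form of AMI, so non-occlusive patients belong to the wider target. Neither set can show how score 2 performs in new arterial patients, and neither helps score 1.

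The size rests on assumptions: the protocol names no cut-off method and no dropping rule. With highly specific signs and 100 per group the excess is only 0.02 to 0.03. The cohort (b) comparison is secondary, since no rule for choosing between the scores is stated and the simulation assumes no subtype differences, which the Background expects. Expert weights would reduce the bias if fixed beforehand, but the protocol brings them in only after the fitted weights have been seen.

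**Conclusion.** The concern holds. Followed as written, the plan reports an AUC that is too high on average for the development steps described, and calls it a test.

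With a real signal the overstatement is about 0.04 to 0.11 at the lower end of the recruitment target and about 0.03 to 0.08 at the upper end, slightly less if the signs are strong. A valueless score could show about 0.64. These sizes assume a best-Youden cut-off search, the stated dropping rules and the listed sign frequencies. They would be smaller with cut-offs and weights fixed in advance, and larger if the interaction approach is used or the arterial set is small. This should be fixed; it does not undermine the data collection or the descriptive aims.

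**What to change.** Make the headline figure an internally validated AUC with a confidence interval. Repeat the cut-off search, weighting and sign dropping in every resample, and the interaction step too if used, written as a fixed rule. Name one method beforehand: repeated stratified 10-fold cross-validation or bootstrap optimism correction. On the figures above cross-validation was closer to the truth; the bootstrap left 0.025 to 0.050 at 50 per group.

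In addition:

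- Label uncorrected values in (a) to (e) as apparent.
- Judge whether a score is useful, whether a simpler version is as good, and any comparison of the two scores in (b), on the corrected AUC.
- If experts replace weights after seeing the data, say that this step cannot be replayed in resamples and that the corrected AUC does not cover it.
- Keeping searched diameter cut-offs or replacing them is the sponsor's choice, provided any search sits inside the resampling.
- Leave-one-site-out prediction, pooled over sites, is an optional extra.

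The cost is some programming and rewording, with no new data. The reported AUC will be lower, the bootstrap leaves some optimism in small subsets, and later external validation is still needed.
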